1. PROTOCOL SUMMARY

Protocol Title: A Phase 3, Randomized, Double-Blind, Placebo-Controlled Study of the Combination of PI3K δ Inhibitor Parsaclisib and Ruxolitinib in Participants With Myelofibrosis

Protocol Number: INCB 50465-313

Objectives and Endpoints:

Table 1 presents the primary and major/key secondary objectives and endpoints.

Table 1: Primary and Secondary Objectives and Endpoints

Objectives	Endpoints
Primary	
To evaluate and compare the efficacy of parsaclisib plus ruxolitinib versus placebo plus ruxolitinib on spleen volume at Week 24.	Proportion of participants achieving $\geq 35\%$ reduction in spleen volume from baseline to Week 24 as measured by MRI (or CT scan in applicable participants).
Major/Key Secondary	
To evaluate and compare the effect of parsaclisib plus ruxolitinib versus placebo plus ruxolitinib on participant reports of MF symptoms.	Proportion of participants who have a $\geq 50\%$ reduction in TSS from baseline to Week 24 as measured by the MFSAF v4.0 diary. Change in TSS from baseline to Week 24 as measured by the MFSAF v4.0 diary. Time to the first $\geq 50\%$ reduction in TSS as measured by the MFSAF v4.0 diary.
To evaluate and compare the effect of parsaclisib plus ruxolitinib versus placebo plus ruxolitinib with respect to OS.	OS determined from the date of randomization until death due to any cause.
To evaluate and compare the safety and tolerability of parsaclisib plus ruxolitinib versus placebo plus ruxolitinib.	Safety and tolerability will be assessed by monitoring the frequency and severity of AEs, performing physical examinations, and evaluating changes in vital signs, ECGs, and laboratory results.

Overall Design:

Table 2 presents the key study design elements. Further study details are presented after the table.

Table 2: Key Study Design Elements

Study Phase	Phase 3
Clinical Indication	Treatment of patients with primary and secondary MF
Population	Participants with primary or secondary MF with DIPSS risk category of intermediate or high who are in need of treatment for MF and are naive to both prior JAK inhibitor and prior PI3K inhibitor therapy
Number of Participants	Approximately 440 participants will be randomized 1:1 to 1 of 2 groups. Note: Certain countries must meet a minimum enrollment regulatory requirement; therefore, enrollment in these countries may continue after enrollment in other countries ends. Group A: pascalisib plus ruxolitinib Group B: placebo plus ruxolitinib

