10.3. Level of Significance

This study defines a single primary endpoint with a single primary analysis. The study will be claimed to have achieved the primary efficacy objective when the primary endpoint shows a significant result at a 2-sided alpha level of 0.05 at final analysis. The secondary efficacy endpoints will be analyzed only when the study has reached the efficacy objective in the primary endpoint. The key secondary efficacy variables will be tested following a fixed-sequence-testing procedure with each at the 2-sided alpha level of 0.05 in the order below:

1. The proportion of participants who have a $\geq 50\%$ reduction from baseline to Week 24 in the MFSAF TSS.
2. OS.

Other secondary [REDACTED] endpoints will be tested using a 2-sided, 5% significance level but are not considered alpha-controlled hypotheses.

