OS adjusted for crossover using rank preserving structural failure time	Inference: Cox regression model including treatment group, baseline (or screening, if applicable) platelet count ($\geq 100 \times 10^9/L$ vs 50 to $< 100 \times 10^9/L$ inclusive), and DIPSS category (intermediate-1 vs intermediate 2 vs high) at randomization	ITT	S
Time to the first $\geq 35\%$ reduction in spleen volume	Inference: Log-rank test with stratification of baseline (or screening, if applicable) platelet count ($\geq 100 \times 10^9/L$ vs 50 to $< 100 \times 10^9/L$ inclusive) and DIPSS (intermediate-1 vs intermediate-2 vs high) at randomization Estimation: Kaplan-Meier	ITT	P
Duration of maintenance of a $\geq 35\%$ reduction in spleen volume	Estimation: Kaplan-Meier	ITT with spleen response	P

Other secondary endpoints, including change and percentage change in MFSAF TSS over time from baseline to Week 24 as measured by the MFSAF v4.0 diary, will be summarized descriptively by treatment group.

For the stratifications of platelet and DIPSS, within a platelet category, in the event that a particular DIPSS stratification level has fewer than 30 participants randomized, it will be combined with the nearest adjacent DIPSS level (eg, Intermediate-1 vs Intermediate-2 vs High). For example, if too small, Intermediate-1 or High risk will be merged with Intermediate-2. If Intermediate-2 has too few participants, then it will be merged with the smaller of the 2 adjacent strata.

In the event that 2 DIPSS stratification levels are combined, a sensitivity analysis for the primary endpoint without combining levels will be conducted.

The primary endpoint will also be compared between treatment groups within each of the following subgroups:

- Baseline platelet count ($\geq 100 \times 10^9/L$ vs 50 to $<100 \times 10^9/L$ inclusive) (Note that if a participant's platelet count is $< 50 \times 10^9/L$ at baseline, the platelet count at screening will be used instead)
- DIPSS category (Intermediate-1 vs Intermediate-2 vs High)
- Sex: male and female
- Age group: ≤ 65 years or > 65 years
- MF type: PMF or PPV-MF/PET-MF
- Presence/absence of V617F mutation at baseline
- Presence/absence of HMR mutations at baseline
- Baseline spleen volume group: \leq median or $>$ median
- Baseline spleen palpation size group: ≤ 10 cm or > 10 cm
- Race: white/Caucasian, black/African American, Asian, American Indian/Alaska Native, Native Hawaiian/Pacific Islander, or other

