2.2. Study Objectives and Endpoints

[Table 1](#) presents the objectives and endpoints.

Table 1: Objectives and Endpoints

Objectives	Endpoints
Primary	
To evaluate and compare the efficacy of parsaclisib plus ruxolitinib versus placebo plus ruxolitinib on spleen volume at Week 24.	Proportion of participants achieving $\geq 35\%$ reduction in spleen volume from baseline to Week 24 as measured by MRI (or CT scan in applicable participants).
Secondary	
To evaluate and compare the effect of parsaclisib plus ruxolitinib versus placebo plus ruxolitinib on participant reports of MF symptoms.	Proportion of participants who have a $\geq 50\%$ reduction in TSS from baseline to Week 24 as measured by the MFSAF v4.0 diary. Change in TSS from baseline to Week 24 as measured by the MFSAF v4.0 diary. Time to the first $\geq 50\%$ reduction in TSS as measured by the MFSAF v4.0 diary.
To evaluate and compare the effect of parsaclisib plus ruxolitinib versus placebo plus ruxolitinib with respect to OS.	OS determined from the date of randomization until death due to any cause.
To evaluate and compare the safety and tolerability of parsaclisib plus ruxolitinib versus placebo plus ruxolitinib.	Safety and tolerability will be assessed by monitoring the frequency and severity of AEs, performing physical examinations, and evaluating changes in vital signs, ECGs, and laboratory results.
To evaluate and compare the time to onset or response and duration of response in spleen volume of participants receiving parsaclisib plus ruxolitinib versus placebo plus ruxolitinib.	Time of onset of a $\geq 35\%$ reduction in spleen volume and duration of maintenance of a $\geq 35\%$ reduction in spleen volume.
[REDACTED]	

Table 1: Objectives and Endpoints (Continued)

Objectives	Endpoints

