3.2. Control of Type I Error

This study defines a single primary endpoint with a single primary analysis. The study will be claimed to have achieved the primary efficacy objective when the primary endpoint shows a significant result at 2-sided alpha of 0.05 at final analysis. The secondary efficacy endpoints will be analyzed only when the study has reached the efficacy objective in the primary endpoint. The key secondary efficacy variables will be tested following a fixed-sequence-testing procedure with each at the 2-sided alpha level of 0.05 in the order below:

1. The proportion of participants who have a $\geq 50\%$ reduction from baseline to Week 24 in MFSAF TSS
2. Overall survival

Other secondary [REDACTED] endpoints will be tested using a 2-sided, 5% significance level; however, these are not considered alpha-controlled hypotheses.

There are 2 planned interim analyses in this study, both aiming to terminate the study if there is inadequate efficacy. The nonbinding futility rules in Interim Analyses 1 and 2 will control the probability of continuing beyond Interim Analysis 2 at 10%. As no formal decision for efficacy will be made based on these interim analyses, no overall alpha will be spent.

An independent DMC will be assembled to monitor safety data, efficacy data, and study conduct on a regular and ongoing basis during the study. See Section 10 for details regarding the alpha-spending plan and interim analyses conducted in this study.

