7.4.2.3. Mean Change and Percentage Change in MFSAF v4.0 Total Symptom Score

The mean change and percentage change from baseline to Week X will be calculated using the following formula:

$$\% \text{ change} = 100 \times (\text{Week X total score} - \text{baseline total score}) / \text{baseline total score}.$$

The mean change and percentage change in TSS, the 7 individual scores, the total score of the 3 spleen-related symptom, including abdominal discomfort, pain under left ribs, and early satiety from baseline to Week X, will be summarized descriptively by treatment group and every 4 weeks using the ITT population. Missing values will not be imputed.

A plot of percentage change from baseline in MFSAF TSS at each visit will be provided.

7.4.2.4. Time to the First $\geq 50\%$ Reduction in Myelofibrosis Symptom Assessment Form v4.0 Total Symptom Score

The time to the first $\geq 50\%$ reduction in TSS is defined as the time from randomization to the first time participants had $\geq 50\%$ reduction in TSS. The daily TSS will be calculated according to the algorithm defined in Section 7.4.2.1.2. Participants with valid calculated baseline TSS and at least 1 postbaseline TSS who do not have $\geq 50\%$ reduction in TSS at the time of analysis will be censored at the time of the last valid calculated TSS. If the participants have no valid calculated baseline or postbaseline TSS, they will be censored at the date of randomization.

The stratified log-rank test will be used to compare time to the first $\geq 50\%$ reduction in TSS between 2 treatment groups in the ITT population at a 1-sided 2.5% significance level, stratified for baseline (or screening, if applicable) platelet count and DIPSS category. The strata identified in the randomization process will be used for the analysis.

Kaplan-Meier curves for time to the first $\geq 50\%$ reduction in TSS will be presented by treatment groups. The KM estimate of median time to the first $\geq 50\%$ reduction in TSS will be presented with its 95% CI. The 95% CI will be calculated using the generalization of method of Brookmeyer and Crowley (1982) with log-log transformation (Klein and Moeschberger 1997).

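### Change in total symptom score to Week 24 is a comparative secondary endpoint said to be tested, but the plan gives only available-case descriptive summaries and no treatment estimate

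*SAP*

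**What the plan says.** - **Objective and endpoint.** SAP 2.2, Table 1 gives the objective as "To evaluate and compare the effect of parsaclisib plus ruxolitinib versus placebo plus ruxolitinib on participant reports of MF symptoms". One of its three endpoints is "Change in TSS from baseline to Week 24 as measured by the MFSAF v4.0 diary". Protocol Tables 1 and 7 carry the same endpoint.
- **General testing statement.** SAP 3.2 says that other secondary "endpoints will be tested using a 2-sided, 5% significance level; however, these are not considered alpha-controlled hypotheses". Protocol 10.3 says the same: "endpoints will be tested using a 2-sided, 5% significance level but are not considered alpha-controlled hypotheses". One or more words in each sentence are blacked out.
- **Specific analysis, Protocol.** Section 10.4.1 reads "Other secondary endpoints, including change and percentage change in MFSAF TSS over time from baseline to Week 24" and says that these "will be summarized descriptively by treatment group". The endpoint has no row in Table 17.
- **Specific analysis, SAP.** Under 7.4.2.3, change and percentage change in the total, the seven items and a three-item spleen score "will be summarized descriptively by treatment group and every 4 weeks using the ITT population". Missing values are left missing. Appendix A plans a by-visit summary (Table 2.2.2.4) and a plot (Figure 4.2.5).
- **Crossover.** SAP 5.1 and 5.2 cut data at early crossover for between-arm analyses. Later data are summarized separately.

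**The concern.** An endpoint attached to a comparative objective should yield an estimate of the treatment difference with its uncertainty. Here the general sections promise a test and the specific sections supply none. If that stays open, the method for comparing mean TSS could be chosen after unblinding.

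The descriptive route has two further weaknesses. First, it uses only the scores that remain, and scores may be lost for reasons linked to symptoms. Second, percentage change divides by a diary baseline that has no minimum and for which 7.4.2.3 gives no zero rule.

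**Working it through.** The documents give no SD, expected difference, power or missing-data rate for mean change in TSS, so there is no planned figure to reproduce. The check is mainly textual, with illustrations under stated assumptions.

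**1. Is change in TSS in the class to be tested?** Yes. The testing sentence is partly blacked out, but Protocol 10.4.1 itself lists change in TSS among the other secondary endpoints. The conflict is inside each document: Protocol 10.3 against 10.4.1, and SAP 3.2 against 7.4.2.3.

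**2. How are the three endpoints under this objective handled?**

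| Endpoint | Planned comparison |
|---|---|
| 50% TSS response at Week 24 (SAP 7.4.2.2) | Stratified CMH test, in the fixed sequence |
| Time to first 50% reduction (SAP 7.4.2.4) | Stratified log-rank test |
| Change in TSS (SAP 7.4.2.3) | None |

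**3. Which scores drop out?** Under Protocol 4.1.3.1, early unblinding before Week 24 needs a rise of at least 25% in spleen volume and ratings of 5 or more on two of three spleen symptoms. Placebo participants then cross over or stop; parsaclisib participants stop. The routes therefore differ by arm and depend partly on symptoms. The responder analysis counts participants who discontinue, are unblinded for crossover or lack a Week 24 score as failures. The mean-change summary leaves out the missing and truncated scores.

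**4. How large could the bias be?** Assume that missing participants differ from observed ones by k SD in both arms. The size of the bias in the observed difference is then k × |m1 − m2|, where m1 and m2 are the missing rates.
- Missing 10% v 10%: 0 for any k that is the same in both arms.
- Missing 20% v 10%: 0.025 SD at k = 0.25; 0.10 SD at k = 1.0.
- Missing 30% v 15%: 0.15 × 0.25 = 0.037 SD; 0.15 × 1.0 = 0.15 SD.

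For scale, the difference detectable with 80% power at two-sided 5% is (1.960 + 0.842) × √(2/n). With 220 per arm it is 0.27 SD. With 10%, 20% and 30% missing in both arms it is 0.28, 0.30 and 0.32 SD.

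**5. What would baseline adjustment gain?** With equal baseline and Week 24 variances and correlation ρ, the variance of the adjusted difference relative to that of an unadjusted change-score difference is (1 + ρ)/2.
- ρ = 0.4: 0.70, a 30% reduction; 1/0.70 = 1.43.
- ρ = 0.6: 0.80, a 20% reduction; 1/0.80 = 1.25.

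If the Week 24 SD is r times the baseline SD, the ratio is r²(1 − ρ²)/(1 + r² − 2ρr). At ρ = 0.5:
- r = 0.8: 0.48/0.84 = 0.57, a 43% reduction.
- r = 1.2: 1.08/1.24 = 0.87, a 13% reduction.

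**6. Can a baseline be zero?** The entry threshold of 10 applies to the recall-based Screening Symptom Form, not to the diary. SAP 7.4.2.2 counts a zero diary baseline as nonresponse; 7.4.2.3 has no equivalent rule. For single items, a total of 10 is compatible with one item at 10 and six at 0, where percentage change is undefined.

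**The case against.** The best defence is that a specific statement overrides a general one. The Protocol and SAP agree that change in TSS is descriptive, and the testing sentence may only set the level for whatever is tested. It cannot cover every secondary endpoint: duration of spleen response has Kaplan-Meier estimation only, and Protocol 10.4.2 plans no formal comparison of laboratory data. This stands in part, since rewording would remove the contradiction. But duration of response is conditional on responding, whereas change in TSS is an ITT comparison under a comparative objective, so the duration precedent does not explain why no estimate is given.

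Four stronger readings are tempting, and the documents do not support them:

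- **The symptom objective goes untested.** It does not: the CMH and log-rank analyses both address it.
- **Only raw means are reported.** SAP 5.1 also includes the number of observations, SD, median and range. A crude difference and interval could be computed from these, and the median percentage change is already produced. What is missing is a prespecified, adjusted contrast.
- **Dropout biases the contrast.** This is possible but not shown, because no rate of discontinuation, crossover or diary loss is given.
- **The plan forgoes the equivalent of 25-43% more participants.** That compares adjustment with a change-score test that the SAP does not plan, and it rests on an assumed correlation and equal variances.

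A mixed model is also not a full cure. It uses observed scores and assumes they are missing at random.

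**Conclusion.** The point holds as a gap between the stated intent and the planned analysis, with modest consequences. Change in TSS has a comparative objective and belongs to a class described as tested, yet the visible text gives no treatment difference, interval, model or missing-data method. Some other sections are blacked out, but this endpoint's own section is visible.

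The primary endpoint, TSS response and overall survival are unaffected, as are the stopping rules. The heading of Protocol Table 1, introduced with "Table 1 presents the primary and major/key secondary objectives and endpoints", does not bring this endpoint under alpha control: the fixed sequence holds only TSS response and overall survival.

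The bias may be nil or may matter. The 0 to 0.15 SD range follows from assumed missing rates and assumed differences between missing and observed participants. The 20-30% variance reduction likewise depends on the assumed correlation of 0.4-0.6 and equal variances; unequal variances move it materially.

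**What to change.** In SAP 7.4.2.3, before unblinding:

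- Add a mixed model for repeated measures on change in TSS at Weeks 4 to 24, with treatment, visit, treatment-by-visit, baseline TSS, platelet stratum and DIPSS. Report the Week 24 difference with a 95% CI, labelled nominal and not alpha-controlled.
- State how scores after discontinuation and after early crossover are handled. Protocol Table 4 continues the diary to Week 24 for early crossovers, so those scores should exist. Protocol 7.1.2 describes safety, subsequent-treatment and survival follow-up after discontinuation without mentioning the diary, so those scores may not.
- State the missing-at-random assumption and add a sensitivity analysis to departures from it.
- Add a zero-baseline rule for percentage change, for the total and the item scores, and lead with the median that SAP 5.1 already provides.
- Align Protocol 10.4.1 with this text. If the sponsor prefers a purely descriptive endpoint, the minimum is to exempt it from the testing sentence in Protocol 10.3 and SAP 3.2.

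The cost is about one SAP paragraph and one table. SAP 7.4.2.1.1 already derives the 4-weekly scores, so the model needs no new data collection. The downside is one more nominal analysis and its missing-at-random assumption.

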7.4.3. Overall Survival

Overall survival is defined as the interval between the randomization date and the date of death due to any cause. Date of death will be determined using the Death Report, the Survival Follow-Up, and the Participant Status eCRFs. Participants who are lost-to-follow-up or still alive at the time of analysis will be right-censored at the earlier of the date the participant was last known alive and the clinical data cutoff date for the analysis. The last known alive date is defined as the later of the last study visit and the date the participant was last known alive from the Survival Follow-Up and Participant Status eCRFs. Partial death dates will be handled using the rules described in Section 4.1.5.

[figure not shown]
The treatment difference in survival for parsaclisib plus ruxolitinib and placebo plus ruxolitinib will be assessed by a log-rank test on the ITT population and PP population stratified for baseline (or screening, if applicable) platelet and DIPSS category. The strata identified in the randomization process will be used for the analysis. In the event that stratification level combinations have limited numbers of participants, 1 or more of the strata may be combined to better facilitate estimation of the overall HR.

[figure not shown]
The hazard ratio estimate and CIs will be estimated based on a stratified Cox proportional hazards model using the same stratification factors as for the log-rank test with Efron's method (1977) accounting for ties in death days.

[figure not shown]
Kaplan-Meier time-to-event curves will be presented by treatment groups. Median survival will be estimated using the KM method. Confidence intervals for median survival time will be calculated using the generalization of Brookmeyer and Crowley's method (1982) with log-log transformation (Klein and Moeschberger 1997).

[figure not shown]
The ITT population will be used for the analysis of OS.

[figure not shown]
A sensitivity analysis of OS will be analyzed using rank preserving structural failure time method to adjust the bias in OS due to crossover.

[figure not shown]

[figure not shown]

9. SAFETY AND TOLERABILITY

[Appendix A](#) provides a list of data displays. Sample data displays are included in a separate document.

9.1. General Considerations

Summary tables may be replaced with listings when appropriate. For instance, an AE frequency table may be replaced with a listing if it only contains a few unique PTs reported on relatively few participants.

Safety analyses for treatment comparisons will exclude data collected after treatment crossover. Data post-treatment crossover will be analyzed separately and descriptively without any treatment comparisons. Day 1 of crossover will be used for the crossover participants in the crossover phase.

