4.1.2. Unblinding and Crossover

When the last enrolled participant has completed the Week 24 assessments and the data entered by all sites for all participants has been verified and cleaned through the Week 24 visit (including imaging), the database will be frozen. The study will then be unblinded, and participants randomized to placebo will have the opportunity to cross over to begin receiving parsaclisib, together with continued ruxolitinib, as long as hematology parameters are adequate (see Section 6.4 for hematology requirements). Similarly, participants found to have been randomized to parsaclisib will continue treatment with parsaclisib, together with continued ruxolitinib, as long as the regimen is tolerated and the participant does not meet discontinuation criteria.

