3.3. Sample Size Considerations

The primary endpoint of this study is the proportion of participants with $\geq 35\%$ spleen volume reduction from baseline to Week 24 as measured by MRI (or CT scan in applicable participants). The primary endpoint will be analyzed by CMH test stratified by DIPSS category (intermediate-1 vs intermediate-2 vs high) and baseline platelet count ($\geq 100 \times 10^9/L$ vs 50 to $< 100 \times 10^9/L$ inclusive). Assuming a 58.2% (29.4%) response rate for participants with normal (low) platelet count for the ruxolitinib plus parsaclisib group versus 41.0% (17.2%) response rate for participants with normal (low) platelet count for the ruxolitinib plus placebo group, to achieve 83.67% power to detect a statistically significant difference with a 2-sided Type I error of 5%, a sample size of 440 participants is required to be randomized equally between treatment groups.

For the key secondary endpoint of proportion of participants who have a $\geq 50\%$ in MFSAF TSS from baseline to Week 24, assuming a response rate of 61.7% (50.0%) for participants with

normal (low) platelet count for the ruxolitinib plus parsaclisib group and a response rate of 45.9% (34.5%) for participants with normal (low) platelet count for the ruxolitinib plus placebo group, a sample size of 440 will provide 80.02% power using CMH test given a 2-sided Type I error of 5%.

A test for OS will be performed when 85 deaths are observed using the log-rank test stratified by platelet count and DIPSS category at baseline at a 2-sided Type I error level of 0.05. The log-rank test will provide 80% power to detect a hazard ratio of 0.54. Assuming a median survival time of 5.3 years for ruxolitinib plus placebo and enrollment duration is 1.5 years, the expected time to analysis from the first participant randomized is 3 years.

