5.2. Treatment Groups

This is a randomized, double-blind, parallel treatment group design. Participants will be summarized by treatment groups. A participant randomized to the control group may make a crossover to the active treatment before Week 24 if the participant met the criteria for an early crossover. Unless specified, efficacy and safety analyses for between-treatment comparisons (parsaclisib + ruxolitinib vs placebo + ruxolitinib) will be conducted using the data truncated at the time of treatment crossover for those participants who made an early treatment crossover before Week 24. Data collected after the treatment crossover will be summarized and tabulated separately without treatment comparisons.

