9.2.3. Adverse Event Summaries

An overall summary of AEs by treatment group will include the following:

- Number (%) of participants who had any TEAEs
- Number (%) of participants who had any serious TEAEs
- Number (%) of participants who had any Grade 3 or higher TEAEs
- Number (%) of participants who had any TEAEs related to parsaclisib
- Number (%) of participants who had any TEAEs related to ruxolitinib
- Number (%) of participants who temporarily interrupted parsaclisib because of TEAEs
- Number (%) of participants who temporarily interrupted ruxolitinib because of TEAEs
- Number (%) of participants who permanently discontinued parsaclisib because of TEAEs
- Number (%) of participants who permanently discontinued ruxolitinib because of TEAEs
- Number (%) of participants who had parsaclisib dose reductions because of TEAEs
- Number (%) of participants who had ruxolitinib dose reductions because of TEAEs
- Number (%) of participants who had any fatal TEAEs

The following summaries will be produced by MedDRA term (if 10 or fewer participants appear in a table, a listing may be appropriate):

- Summary of TEAEs by MedDRA SOC and PT
- Summary of TEAEs by MedDRA PT in decreasing order of frequency
- Summary of TEAEs by MedDRA SOC, PT, and CTCAE grade category
- Summary of Grade 3 or higher TEAEs by MedDRA SOC and PT
- Summary of Grade 3 or higher TEAEs by MedDRA PT in decreasing order of frequency
- Summary of serious TEAEs by MedDRA SOC and PT
- Summary of serious TEAEs by MedDRA PT in decreasing order of frequency
- Summary of parsaclisib treatment-related TEAEs by MedDRA SOC and PT

- Summary of ruxolitinib treatment-related TEAEs by MedDRA SOC and PT
- Summary of parsaclisib treatment-related TEAEs by MedDRA PT in decreasing order of frequency
- Summary of ruxolitinib treatment-related TEAEs by MedDRA PT in decreasing order of frequency
- Summary of parsaclisib treatment-related TEAEs by MedDRA SOC, PT, and CTCAE grade category
- Summary of ruxolitinib treatment-related TEAEs by MedDRA SOC, PT, and CTCAE grade category
- Summary of Grade 3 or higher parsaclisib treatment-related TEAEs by MedDRA SOC and PT
- Summary of Grade 3 or higher ruxolitinib treatment-related TEAEs by MedDRA SOC and PT
- Summary of parsaclisib treatment-related serious TEAEs by MedDRA SOC and PT
- Summary of ruxolitinib treatment-related serious TEAEs by MedDRA SOC and PT
- Summary of TEAEs with a fatal outcome by MedDRA SOC and PT

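### After study-wide unblinding, the safety comparison stops counting placebo participants who cross over but not the parsaclisib arm, so crude adverse event percentages rest on unequal follow-up and can show a false excess on parsaclisib

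*SAP*

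**What the plan says.** SAP 9.1 sets the rule for between-arm safety tables: "Safety analyses for treatment comparisons will exclude data collected after treatment crossover". What follows crossover is kept apart: "Data post-treatment crossover will be analyzed separately and descriptively without any treatment comparisons". SAP 5.2 words the truncation more narrowly. There, efficacy and safety comparisons are "conducted using the data truncated at the time of treatment crossover for those participants who made an early treatment crossover before Week 24", unless otherwise specified.

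Protocol 4.1.2 opens crossover to the whole placebo arm at study unblinding. The trigger is "When the last enrolled participant has completed the Week 24 assessments", followed by data cleaning and a database freeze. Then "participants randomized to placebo will have the opportunity to cross over to begin receiving parsaclisib", subject to blood count limits, while "participants found to have been randomized to parsaclisib will continue treatment with parsaclisib".

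The overall adverse event summary in SAP 9.2.3 is a list of counts with percentages, for example "Number (%) of participants who had any serious TEAEs". Grade 3 or higher, fatal and discontinuation events are handled in the same way. Life-table versions are planned for all treatment-emergent events only, by preferred term and by system organ class with preferred term (Appendix A, Tables 3.2.18 and 3.2.19). Kaplan-Meier time to first onset is planned for each event of special interest (SAP 9.2.2, Table 3.2.20.2). SAP 6.4 summarizes duration of treatment, but no table uses it as a denominator for event rates.

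**The concern.** Crossover is possible in one direction only, so the exclusion in SAP 9.1 shortens comparative follow-up in one arm only. Nothing in either document ends the parsaclisib arm's contribution at a matching time. A crude percentage grows with time at risk. At a cut made after study-wide unblinding, the arm observed longer will therefore tend to show more participants with an event even when the drug adds no risk.

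The affected tables are the ones most readers use for benefit-risk. A difference in follow-up could be read there as drug toxicity, or could obscure how much of a real difference is drug effect.

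**Working it through.** **Timeline.** The documents give no safety follow-up figure, so the timeline comes from the survival assumptions in SAP 3.3: "enrollment duration is 1.5 years, the expected time to analysis from the first participant randomized is 3 years". That section also gives 85 deaths, a control median of 5.3 years and a hazard ratio of 0.54. With uniform accrual over 1.5 years, exponential survival and 220 per arm, expected deaths are 84.6 at 2.9 years and 88.1 at 3.0 years. The 3-year horizon therefore reproduces. The earliest possible study unblinding is 1.5 years + 24 weeks = 1.96 years. I use 2.1 years to allow for cleaning and the freeze.

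**Assumptions not in the documents.** The first-event hazard λ is constant and equal in both arms, so the true excess is zero. Discontinuation occurs at rate δ. All placebo participants cross over, except where stated.

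**Formula.** With uniform accrual over 1.5 years and comparative follow-up ending at calendar time T, let k = λ + δ. The crude percentage is

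P(T) = (λ/k) × {1 − [e^(−k(T−1.5)) − e^(−kT)] / (1.5k)}.

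The parsaclisib arm has T = 3. Placebo participants who cross have T = 2.1.

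1. *λ = 0.2, δ = 0.*
   - Parsaclisib: 1 − (0.7408 − 0.5488)/0.3 = 36.0%.
   - Placebo: 1 − (0.8869 − 0.6570)/0.3 = 23.4%.
   - The ratio is 1.54. Mean follow-up is 2.25 vs 1.35 years.
2. *λ = 0.2, δ = 0.25 in both arms (k = 0.45).*
   - Parsaclisib: 0.444 × {1 − (0.5092 − 0.2592)/0.675} = 28.0%.
   - Placebo: 0.444 × {1 − (0.7634 − 0.3887)/0.675} = 19.8%.
   - The ratio is 1.42. Mean exposure is 1.71 vs 1.13 years.
3. *Range of λ.* Across 0.1 to 0.5/year and these two discontinuation settings, the ratio runs from 1.6 down to 1.3.
4. *Partial crossover, δ = 0.* This assumes that those who do not cross stay in the comparison.
   - At 80% crossing, placebo is 0.8 × 23.4 + 0.2 × 36.0 = 25.9% (ratio 1.39).
   - At 50% crossing, placebo is 29.7% (ratio 1.21).
5. *Very frequent events.* At λ = 3/year and δ = 0 the result is 99.8% vs 96.4%. Crude incidence saturates and little bias remains.
6. *Unequal discontinuation.* Here λ = 0.2, crossover is at 1.96 years, 80% cross and placebo discontinuation is 0.3/year.

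| Parsaclisib discontinuation | Parsaclisib | Placebo | Difference (points) |
|---|---|---|---|
| 0.3/year | 26.7% | 19.5% | +7.3 |
| 0.6/year | 20.6% | 19.5% | +1.2 |
| 0.9/year | 16.5% | 19.5% | −3.0 |

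(Differences are taken before rounding.)

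7. *Cut at the Week 24 freeze.* Study-wide crossover has not yet happened. If 2% to 10% of placebo participants crossed early and were truncated at Week 12, the false excess is 0.2 to 0.9 points at 0.1/year and 0.7 to 3.3 points at 0.5/year.
8. *Common cutoff.* With both arms truncated at 2.1 years, case 1 becomes 23.4% vs 23.4%.

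**Do the planned adjusted summaries repair this?** The life-table rule in SAP 9.2.1 censors by reference to last dose of study drug and last visit. For a participant who crossed over, both dates fall after crossover. The special-interest rule in SAP 9.2.2 censors event-free participants at the time of analysis. Read literally beside SAP 9.1, both rules credit those who crossed with event-free time in which their events are not counted. No life-table version covers serious, Grade 3 or higher, fatal or discontinuation events.

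**The case against.** The strongest reply is that the main safety comparison may never be exposed to this. Study-wide crossover starts only after the Week 24 database is cleaned and frozen. A safety comparison at that freeze carries only the small early-crossover effect, and the Week 24 wording in SAP 5.2 suggests that this may be the cut intended. The documents do not say that comparative safety tables are rerun at the survival analysis, and that test is reached only if the primary and symptom endpoints both succeed (Protocol 10.3). This stands as a limit on the point. It does not remove it. No safety cutoff is stated, SAP 9.1 covers any crossover, and it provides for a crossover phase in reporting. The table shells, which might settle the cut, are in a separate document.

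Three stronger readings are tempting and are not supported:

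- *The bias always runs against parsaclisib.* It does so when discontinuation is similar between arms. Participants found to be on parsaclisib at early unblinding must stop both drugs (Protocol 4.1.3), which shortens that arm's follow-up. Enough extra discontinuation shrinks or reverses the gap, as the table shows.
- *The SAP relies on crude percentages alone.* It does not. It plans life-table and Kaplan-Meier summaries and reports exposure. The defect is in their coverage and censoring rules.
- *The base-case size is a forecast.* It assumes that every placebo participant crosses. Protocol 4.1.2 offers crossover as an option, and Protocol 6.4 sets platelet and neutrophil conditions. Events concentrated early in treatment would also show less imbalance than a constant hazard implies.

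**Conclusion.** The point holds for data cuts after study-wide unblinding. Following SAP 9.1 as written, crude between-arm percentages at such a cut compare unequal follow-up and can show a false excess on parsaclisib.

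At 3 years with a common hazard of 0.2/year, the spurious gap is about 8 to 13 points when all placebo participants cross and discontinuation is equal (28.0 − 19.8 = 8.2; 36.0 − 23.4 = 12.6). It is about 10 points at 80% crossing with no discontinuation (36.0 − 25.9 = 10.1). Event rates, discontinuation and crossover share are my assumptions, so the size is illustrative. The asymmetry itself follows from the text. At the Week 24 freeze the effect is confined to early crossover, about 0.2 to 3.3 points over the ranges tried.

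A reader might infer that the trial's headline safety result is bound to be biased. The documents do not support that, because they leave the cut unstated. The plan should be amended, but this does not invalidate the design.

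**What to change.** 1. State the data cutoff for the comparative safety tables.
2. For between-arm tables at cuts after unblinding, truncate both arms at the study unblinding date. Alternatively, report exposure-adjusted incidence per 100 patient-years beside each crude percentage for serious, Grade 3 or higher, fatal, discontinuation and special-interest events. In either case, show later parsaclisib-arm data separately.
3. Name crossover as a censoring time in the life-table rule (SAP 9.2.1) and in the Kaplan-Meier rule for events of special interest (SAP 9.2.2).
4. Align SAP 5.2 with 9.1 so that both describe the same crossover events.

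The cost is SAP wording and some added table columns. No new data are needed.
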